### 6.3.3 Medications Used with Caution

No data exist regarding the interaction of NT-I7 with drugs known to prolong the QT/QTc interval. Accordingly, subjects receiving these drugs while receiving NT-I7 therapy should be closely monitored.

## 6.4 Duration of Therapy

In the absence of treatment delays due to adverse event(s), treatment may continue for *up to 27 weeks (4 cycles/doses)* or until one of the following criteria for discontinuation of therapy applies:

- Disease progression requiring systemic therapy
- Intercurrent illness that prevents further administration of treatment

- Unacceptable adverse event(s)
- Dose limiting toxicity
- Participant decides to withdraw from the study
- General or specific changes in the patient's condition render the patient unacceptable for further treatment in the judgment of the investigator
- Participant not adhering to study schedule and procedures
- Dosing interruption lasting >12 weeks
- Pregnancy
  - All women of child bearing potential should be instructed to contact the investigator immediately if they suspect they might be pregnant (e.g., missed or late menstrual period) at any time during study participation.
  - The investigator must immediately notify CITN in the event of a confirmed pregnancy in a patient participating in the study.
- Termination of the study by sponsor
- The drug manufacturer can no longer provide the study agent

The reason(s) for protocol therapy discontinuation, the reason(s) for study removal, and the corresponding dates must be documented in the Case Report Form (CRF).

## 6.5 Study Treatment Beyond Progression

Immunotherapeutic agents such as NT-I7 may produce antitumor effects by potentiating endogenous cancer-specific immune responses. The response patterns seen with such an approach may extend beyond the typical time course of responses seen with cytotoxic agents and can manifest as a clinical response after an initial increase in tumor burden or even the appearance of new lesions.

Patients may be treated beyond progression as measured by ACTG criteria up to 4 doses if they meet all of the following criteria:

- There is no indication for chemotherapy
- The PI suspects increases in lesion measurements may be due to pseudoprogression based on assessment of changes in tumor burden and tumor associated symptoms
- The patient is tolerating therapy without DLTs

- There is no decrement in performance status
- There is absence of symptoms and signs indicating clinically significant progression of disease
- There is absence of symptomatic rapid disease progression requiring urgent medical care

These criteria must be met to ensure that patients are not exposed to unreasonable risks by continued use of the investigation agent in spite of progression of disease.

Subjects should remain on the trial and continue to receive monitoring according to the Study Calendar ([Section 11](#)). In addition to routine monitoring, participants with KS progression will be evaluated in 4 weeks ( $\pm 1$  week) for follow-up tumor assessment and possible removal from study.

At the time of progression of disease, patients will be re-consented and adequately informed of all FDA-approved therapy and potential clinical benefit that the patient may be foregoing in order to continue receiving the investigational product.

## **6.6 Duration of Follow-Up**

The active study will end when the last participant reaches 2 years.

Participants will be followed every 12 weeks for 12 months after the final dose of NT-I7, regardless of number of doses, to evaluate durability of T cell and tumor response. Participants will be taken off study after completing the 12 months of follow-up after final dose of NT-I7, or at investigator discretion or participant preference.

End of treatment visit should be performed 7 days after the last administration of either agent or immediately before initiation of any other cancer therapy.

After disease progression or start of new anticancer treatment, subject will be followed for survival every 12 weeks ( $\pm 1$  week) until death, lost to follow-up, withdrawal of consent or the end of the study, whichever occurs first. Survival follow-up can be done either by in-person visit or by telephone assessment.

Subjects removed from study for unacceptable AE(s) will be followed until resolution or stabilization of the AE; in addition, the subjects will be followed for disease status and overall survival, as described above.

## **6.7 Patients Lost to Follow-Up**

A subject will be considered lost to follow-up if he or she repeatedly fails to return for scheduled visits and is unable to be contacted by the study site.

The following actions must be taken if a subject fails to return to the clinic for a required study visit:

- The site must attempt to contact the subject and reschedule the missed visit as soon as possible and counsel the subject on the importance of maintaining the assigned visit schedule and ascertain whether or not the subject wishes to and/or should continue in the study.
- Before a subject is deemed lost to follow-up, the investigator or designee must make every effort to regain contact with the subject (where possible, 3 telephone calls and, if necessary, a certified letter to the subject's last known mailing address or local equivalent methods). These contact attempts should be documented in the subject's medical record.
- Should the subject continue to be unreachable, he/she will be considered to have withdrawn from the study.

## 7. DOSING DELAYS/DOSE MODIFICATIONS

The NCI CTCAE Version 5.0 will be used to grade AEs. Subjects enrolled in this study will be evaluated clinically and with standard laboratory tests before and at regular intervals during their participation in this study as specified in this section.

Subjects will be evaluated for treatment-emergent adverse events (all grades), SAEs and AEs requiring study drug interruption or discontinuation at each study visit for the duration of their participation in the study.

Clinical experience has demonstrated that development of autoimmune inflammatory conditions is a general risk with therapeutics intended to enhance anti-tumor T-cell responses. Such immune related AEs (irAEs) have been described for virtually all organ systems and include, but are not limited to, colitis, hepatitis, pneumonitis, endocrinopathy, ocular toxicity, pancreatic toxicity and rash.

The risk of development of autoimmune inflammatory condition related to NT-I7 seems relatively low. In the previous clinical studies with rhIL-7 and in the studies with single-agent NT-I7, including the completed FIH study GX-I7-HV-001 in normal healthy individuals with NT-I7, no irAEs were reported. In the completed study GX-I7-CA-003 in patients with advanced solid tumors one AE suggestive of autoimmune disease was reported. In the ongoing study NIT110, immune-mediated hepatitis and immune-mediated nephritis were reported as adverse drug reactions in patients receiving NT-I7 in combination with pembrolizumab.

Immune-related toxicities associated or possibly associated with NT-I7 should be closely monitored and carefully managed according to standard medical practice (e.g., thyroid hormone replacement for autoimmune hypothyroidism). Additional tests, such as autoimmune serology or biopsies, should be used to determine a possible immunogenic etiology. Although most irAEs observed with immune modulatory agents have been mild and self-limiting, such events should be recognized early and treated promptly to avoid potential major complications ([Di Giacomo, Biagioli, and Maio 2010](#)). Discontinuation of NT-I7 may not have an immediate therapeutic effect, and there is no available antidote for NT-I7. The primary approach to mild irAEs (Grades

1–2) is supportive and symptomatic care. In severe cases, irAEs may be acutely managed with systemic corticosteroids, mycophenolate or TNF- $\alpha$  antagonists.

Due to the potential risk of NT-I7 to induce autoimmune conditions, patients with a history of clinically significant autoimmune disease will be excluded from this trial.

### **Dose modifications for Adverse Events:**

Adverse Events from NT-I7 are expected to be mild and infrequent, as well as transient and Grade 2 or less (as noted in the AE list, [Section 10](#)). If a patient experiences a clinically significant and/or unacceptable toxicity, dosing should be interrupted, or the dose should be reduced per guidelines below and supportive therapy administered per standard clinical practice.

A maximum of two dose reductions will be allowed for an individual patient. If the second dose reduction is not tolerated, study treatment should be permanently discontinued, and the patient should be followed for safety per protocol guidelines.

NT-I7 administration will be held if the ALC is greater than 10,000 cells/ $\mu$ L. A blood draw will be performed prior to dosing on Day 1 of each cycle. Elevated ALC levels which have not resolved to  $\leq$  Grade 1 and/or requiring more than a 72-hour delay in administration of NT-I7 must be discussed with the Study Sponsor. Grade 3 lymphocyte count increase ( $>20,000$  cells/ $\mu$ L) is a normal physiologic response to the study treatment.

Below are dose management tables for the following AEs: fatigue, nausea, vomiting, diarrhea, neutropenia, thrombocytopenia, and hepatic damage.

Event Name	Fatigue
Grade of Event	Management/Next Dose for NT-I7
$\leq$ Grade 1	No change in dosing schedule
Grade 2	No change in dosing schedule
Grade 3	Hold* until $\leq$ Grade 2
Grade 4	Off protocol therapy

\*Patients requiring a delay of  $>72$  hours should go off protocol therapy.

Recommended management: physician discretion

Event Name	Nausea
Grade of Event	Management/Next Dose for NT-I7
$\leq$ Grade 1	No change in dosing schedule
Grade 2	No change in dosing schedule
Grade 3	Off protocol therapy if with adequate/maximal medical intervention symptoms persist
Grade 4	Off protocol therapy

Patients requiring a delay of  $>72$  hours should go off protocol therapy.

Recommended management: antiemetics

Event Name	Vomiting
Grade of Event	Management/Next Dose for NT-I7
≤ Grade 1	No change in dosing schedule
Grade 2	No change in dosing schedule
Grade 3	Off protocol therapy if with adequate/maximal medical intervention symptoms persist
Grade 4	Off protocol therapy
Patients requiring a delay of >72 hours should go off protocol therapy.	
Recommended management: antiemetics	

Event Name	Diarrhea
Grade of Event	Management/Next Dose for NT-I7
≤ Grade 1	No change in dosing schedule
Grade 2	No change in dosing schedule
Grade 3	Off protocol therapy if with adequate/maximal medical intervention symptoms persist
Grade 4	Off protocol therapy
Patients requiring a delay of >72 hours should go off protocol therapy.	
Recommended management: physician discretion	

Event Name	Neutropenia
Grade of Event	Management/Next Dose for NT-I7
≤ Grade 1	No change in dosing schedule
Grade 2	No change in dosing schedule
Grade 3	Hold* until ≤ Grade 2
Grade 4	Off protocol therapy
*Patients requiring a delay of >72 hours should go off protocol therapy.	
Recommended management: treatment of infection as appropriate	

Event Name	Thrombocytopenia
Grade of Event	Management/Next Dose for NT-I7
≤ Grade 1	No change in dosing schedule
Grade 2	No change in dosing schedule
Grade 3	Off protocol therapy
Grade 4	Off protocol therapy
Patients requiring a delay of >72 hours should go off protocol therapy.	
Recommended management: platelet transfusion if indicated	

Event Name	Hepatic Damage
Grade of Event	Management/Next Dose for NT-I7
≤ Grade 1	No change in dosing schedule
Grade 2	No change in dosing schedule 
Grade 3	Off protocol therapy
Grade 4	Off protocol therapy
Patients requiring a delay of >72 hours should go off protocol therapy.	
Recommended management: physician discretion	

Event Name	HIV Viremia
Grade of Event	Management/Next Dose for NT-I7
HIV RNA > lower limit of detection and 400 copies /mL	No change in dosing schedule. Monitor HIV viral load 4 weeks later.
HIV RNA >400-1000 copies/mL	Repeat measurement in 4 weeks. Hold next cycle until plasma HIV RNA < 400 copies/mL. Evaluate adherence to medication.
HIV RNA >1000 copies/mL	Repeat measurement in 4 weeks. Hold next cycle until plasma HIV RNA < 400 copies/mL. If repeat > 1000 copies/mL, evaluation for HIV drug resistance
DLT (Section 6.2.1.)	Off protocol therapy
Patients requiring a delay of >72 hours should go off protocol therapy.	
Recommended management: physician discretion	

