**Figure 2. Effects of subcutaneous injections of r-hIL-7 on gut mucosal T-cells at week 12 in people with HIV**

*PLoS Pathogens*, Volume 10, Issue 1, Jan 2014.  
<https://journals.plos.org/plospathogens/article?id=10.1371/journal.ppat.1003890>

HIV viremia (“blips”) that were of unclear significance. This was followed by a phase II study of IL-7 in patients with HIV observed HIV RNA blips >50 copies/mL, occasionally exceeding 200 copies/mL, which prompted delay of subsequent IL-7 doses ([Thiebaut et al. 2016](#)). The clinical relevance of these viral “blips” is unclear; it is possible that it represents expansion of T cells but not replication-competent HIV. Experience to date suggests “blips” are short lived, lasting less than 4 weeks in ACTG5214.

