Biopsy Specimen Collection		X q			X r	X s			X r		
Correlative Studies Bloodt											
T cell (CD4+ and CD8+) count		X	X	X	X	X	X				
Immunogenicity: ADA and NADA		X			X		X	X	X		
Immunophenotyping		X u	X u	X u	X u	X u	X u				
KSHV Humoral Responses		X u		X u	X u				X u		
KSHV PBMC Viral Load		X		X	X				X		
Anti-KSHV Immune T-cell Response		X u			X u				X u		
TCR Clonality		X		X	X		X	X			
IL-7		X		X	X		X	X			
NT-I7 PK w		X w	X		X w		X w	X w	X		

- a. Treatment cycle: A given dose level of NT-I7 will be administered on Day 1 (±2 days) of each 9-week cycle (4 doses).
- b. End of treatment (EOT) visit should be performed on week 36 (±7 days), or ≤ 7 days after the last dose of IP, or immediately before initiation of a new anticancer therapy for participants who require therapy before week 36, whichever is sooner.
- c. Follow-up visit should be performed 30 days (±7 days) after the last dose of IP, and before subsequent therapy for participants who come off treatment before week 36 due to progressive disease, as well as for those who come off treatment before week 36 for reasons other than progression.
- d. Disease assessment per standard of care every 12 weeks (±7 days) for 12 months. Study participants who start new anticancer treatment or discontinue study treatment due to documented disease progression will be followed for survival only every 12 weeks (±1 week) until death, lost to follow-up, withdrawal of consent or the end of the study, whichever occurs first. Survival follow-up can be done either by in-person visit or by telephone assessment.
- e. Three dose levels of NT-I7 will be administered, 480 µg/kg, 960 µg/kg and 1200 µg/kg injected on the first day (± 2 days) of every cycle.
- f. Written informed consent and any locally required privacy act document authorization must be obtained prior to performing any protocol-specific procedures, including screening evaluations. The written informed consent includes genetic sample collection and analysis. Informed consent and other administrative procedures must be performed within 28 days of treatment initiation.

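### In the HIV viremia table, the 72-hour line ends treatment before the 4-week repeat that could release a held dose

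*Combined protocol and SAP*

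**What the plan says.** The HIV viremia table in Section 7 has three tiers. Detectable values up to 400 copies/mL leave dosing unchanged. For values >400 to 1000 the instruction is "Repeat measurement in 4 weeks. Hold next cycle until plasma HIV RNA < 400 copies/mL. Evaluate adherence to medication". Above 1000 the repeat and the hold are the same, and a repeat still >1000 leads to a resistance work-up. A further row takes participants with a DLT under Section 6.2.1 off therapy. Beneath these rows stands: "Patients requiring a delay of >72 hours should go off protocol therapy".

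The same 72-hour sentence closes the other tables in Section 7. In the two others that order a hold (fatigue and neutropenia) an asterisk ties it to the hold, as in "Hold* until ≤ Grade 2". The HIV hold rows carry no asterisk, and HIV viremia is missing from the list of events that introduces the tables. Section 7 offers discussion with the sponsor for delays beyond 72 hours, but only for a raised lymphocyte count. Among the grounds for ending treatment, Section 6.4 lists "Dosing interruption lasting >12 weeks".

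On DLTs, item 5 of Section 6.2.1 includes an AIDS-defining opportunistic infection with new viremia >400 copies/mL lasting over 90 days. A DLT must occur in the first 28 days, and the cohort is reviewed once all its members have completed that window.

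**The concern.** The table orders two things that cannot both be done. A hold that waits for a measurement 4 weeks away cannot be released if treatment ends after 3 days. The row for values >1000 plans an action at the repeat, which suggests that resumption was in view. The 72-hour line may simply have been carried over from the other tables, but that is inference and a site cannot rely on it.

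With the same pre-dose viral load, one site could hold, repeat and redose while another ends treatment. That changes how many doses a participant receives in a trial of up to 20, and so the multi-dose safety, T-cell and response data that each participant contributes.

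The related DLT issue is smaller. The only DLT criterion that names HIV needs more time than the cohort review allows. The HIV table's off-therapy row relies on that windowed list, although doses 2 to 4 are all given later.

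**Working it through.** The plan gives no figure to reproduce; the check is calendar arithmetic.

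**Inputs**
- Doses at Weeks 0, 9, 18 and 27, each ±2 days (Section 6; Section 11, footnote a).
- HIV viral load at screening, Weeks 0, 4, 9, 13, 18 and 27, and end of treatment (EOT) (Section 11).
- After Cycle 1, laboratory tests may be drawn up to 72 h early (Section 11, footnote k).
- Repeat interval 4 weeks = 28 days = 672 h (Section 7).
- Limits: 72 h (Section 7) and 12 weeks = 84 days (Section 6.4).

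**Delay = day of the releasing repeat − due day D of the dose**

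1. *Clears at the mid-cycle repeat.* Week 4 + 4 = Week 8, before Week 9; Week 13 + 4 = Week 17, before Week 18. Delay 0.
2. *Dose-day value that governs only the following cycle and clears at its repeat.* Week 9 + 4 = Week 13, before Week 18; Week 18 + 4 = Week 22, before Week 27. Delay 0.
3. *Persists at the last repeat before a dose (Week 8, 17 or 26), and the dose-day sample does not clear it.* If the 4-week interval repeats (an assumption), the next result is at Week 12, 21 or 30. That is 3 weeks after the due dose: 21 days = 504 h; 504/72 = 7.0 times the limit.
4. *Found before dosing at Week 9, 18 or 27.* Sample on D: repeat at D+28 = 672 h; 672/72 = 9.3 times. Sample at D−3: repeat at D+25 = 600 h; 600/72 = 8.3 times.
5. *Every window taken to shorten the delay.* Case 4: visit 2 days early and sample 3 days before it (D−5), so the repeat is at D+23; less the 2-day late dosing window = 21 days (504 h, 7.0 times). Case 3, starting from Week 13: 21 − 5 − 2 = 14 days = 336 h; 336/72 = 4.7 times.

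Whenever a dose is held, the ordered repeat misses the 72-hour limit by a wide margin. Stopping at Week 9, 18 or 27 forfeits 3, 2 or 1 of the 4 planned doses.

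**Room under a 12-week cap**
- Counted from the due dose (84 days), repeats fall at days 28/56/84, 25/53/81 or 21/49/77. Three fit in each case, one of them exactly on the limit.
- Counted from the previous dose, 12 − 9 = 3 weeks (21 days) remain.
- A Week 27 dose held for the full period moves to 27 + 12 = Week 39, past the Week 36 EOT visit. A Week 18 dose moves to Week 30, past the nominal Week 27 dose.

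**The 90-day DLT criterion**
- Participants enter at ≤40 copies/mL (Section 3.1.5), so the viremia must be new. Starting at dose 1, it reaches 90 days 90 − 28 = 62 days after a Day 28 review. If the window is read as Week 0 Day 1 through Week 4 Day 7 (35 days, Section 9.1.1.1), the gap is 90 − 35 = 55 days.
- Even if it began at the earliest screening day (−28), it could have lasted at most 28 + 28 = 56 days, or 35 + 28 = 63 days, by the review. Both are under 90.
- The first post-dose viral load is at Week 4. On scheduled or ordered samples, 90 days from then is first covered by the Week 17 repeat of a Week 13 value: 13 × 7 = 91 days.

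**The case against.** Several points on the other side stand.

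- *The clash is narrow.* A reader might infer that any value >400 ends treatment. The documents do not support that: with 9-week cycles, cases 1 and 2 above cause no delay. An earlier unscheduled retest is not forbidden, and the table leaves management to the physician. But none is ordered, so a site following the table has no result within 72 hours.
- *The background on blips does not settle it.* A reader might infer from Section 2.1.5 that short-lived blips would cost participants their treatment. Blips in the earlier phase II IL-7 study were >50 copies/mL, "occasionally exceeding 200 copies/mL, which prompted delay of subsequent IL-7 doses". Values up to 400 fall in the tier that leaves dosing unchanged. The remark that blips were "short lived, lasting less than 4 weeks in ACTG5214" gives no magnitude, so it does not show that values >400 are brief.
- *Section 6.4 need not conflict.* It lists several grounds for stopping, and a 12-week outer limit can coexist with a shorter event-specific one. The contradiction is inside the HIV table.
- *Stopping could be a deliberate safety choice.* Ending an IL-7 agent in a participant with sustained viremia is defensible in phase 1. The table would then have to say so, and the hold-until-clear instruction would have no purpose once a dose is due.
- *Little of the primary analysis is touched.* DLTs are judged after dose 1, and the Week 9 biopsy precedes dose 2.

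On the DLT criterion, a reader might infer that serious HIV events after Day 28 go unmonitored. That is too strong. Within the window, items 1, 7 and 8 of Section 6.2.1 capture related Grade ≥3, treatment-ending or fatal events. Later, Section 6.4 allows stopping for an unacceptable adverse event or intercurrent illness, and Section 9.1.1.1 brings later adverse events into the RP2D decision. Section 2.4.1 also promises stopping rules for AIDS-defining events, but it is rationale text and no later section turns that promise into an HIV-specific rule beyond the window.

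**Conclusion.** The main point holds, limited to doses that are actually held. On the schedule the table orders, the repeat falls about 21 to 28 days after the due dose, and no less than 14 days under the most favourable windows, against a 72-hour limit. Hold-and-resume therefore cannot operate, and nothing else in the protocol says which instruction governs. This rests on sites following the ordered 4-week interval, with no earlier retest, and, for the 21-day case, on that interval repeating. The documents give no rate of values >400 copies/mL, so no number of affected participants can be stated. The consequence is confined to doses 2 to 4. It should be fixed because a stated rule is inoperable and the remedy is short.

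The DLT point is true but minor: the 90-day criterion cannot inform its own cohort's escalation decision, and the HIV off-therapy row does not reach an infection that begins after the window.

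**What to change.** 1. Delete the 72-hour sentence from the HIV viremia table only, so that the hold until <400 copies/mL governs.
2. Cap that hold at the 12-week interruption limit in Section 6.4, and state that the 12 weeks count from the due dose.
3. State that later doses, visits and EOT shift with a delayed dose. Without this, the Week 36 EOT visit could precede a dose delayed from Week 27.
4. Point the off-therapy row of the HIV table to an AIDS-defining infection with persistent viremia at any time on treatment, and have such events considered in the RP2D decision. This would put the intention of Section 2.4.1 into effect.

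The cost is amendment wording. The viral loads are already scheduled, Section 7 already orders the 4-week repeats, and no cohort waits longer. A held participant's calendar would run later than planned, and item 4 adds a stopping ground rather than only correcting a reference. The small downside is that a viremic participant stays eligible to resume for up to 12 weeks, but no drug is given while HIV RNA is not <400 copies/mL.

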### 3. PATIENT SELECTION

#### 3.1 Eligibility Criteria

- 3.1.1 Patients must have histologically confirmed Kaposi sarcoma.
- 3.1.2 Patients must have evaluable disease.  
Note: Kaposi sarcoma will be evaluated using a modified version (consistent with NCI studies) of the AIDS Clinical Trial Group (ACTG) Oncology Committee staging and response definitions for KS.
- 3.1.3 No upper or lower limit on the number of prior therapies or stage of disease. No prior systemic therapy (other than ART for HIV) or local therapy is required.
- 3.1.4 HIV-positive patients must have been on effective anti-retroviral (ART) therapy for at least 3 months prior to enrollment, with persistent KS affecting quality of life due to

either T1 disease or T0 disease with inadequate disease regression on ART alone.

3.1.5 HIV-positive patients must have undetectable HIV viral loads  $\leq$ 40 copies/mL measured using an FDA-approved commercial assay with lower limit of detection between  $\leq$ 20 copies/mL and  $\leq$  40 copies/mL.

3.1.6 Patients with visceral involvement must:

- Meet other eligibility criteria
- Have any/all associated tumor associated symptoms  $\leq$  Grade 2 by CTCAE criteria; and/or
- Require no immediate intervention (e.g., mild oozing of oral KS not an exclusion criteria)

3.1.7 Patients must provide newly obtained core, punch, or excisional biopsy of a tumor lesion obtained up to 28 days prior to treatment initiation. An archival tumor sample obtained within 1 year of screening is allowed if pre-treatment biopsy is deemed unsafe or technically not feasible.

3.1.8 Patients must be  $\geq$ 18 years of age on day of signing informed consent document. Because no dosing or adverse event data are currently available on the use of NT-I7 in patients  $<$ 18 years of age, children are excluded from this study but will be eligible for future pediatric trials.

3.1.9 ECOG performance status  $\leq$ 2 (Karnofsky  $\geq$ 60%, see [Appendix A](#)).

3.1.10 Patients must have adequate organ and marrow function as defined below:

- leukocytes	$\geq$ 2,500/mcL
- absolute neutrophil count	$\geq$ 1,000/mcL
- platelets	$\geq$ 100,000/mcL
- hemoglobin	$\geq$ 9/dL
- total bilirubin	$\leq$ 1.5 institutional upper limit of normal (ULN) OR $<3 \times$ institutional ULN for Gilbert's syndrome or HIV protease inhibitors
- AST(SGOT)/ALT(SGPT)	$\leq$ 2.5 $\times$ institutional ULN
- creatinine	$\leq$ 2 $\times$ institutional ULN OR

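### In the HIV viremia table, a due dose held for the ordered 4-week repeat is always overtaken by the table's own 72-hour stopping line

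*Combined protocol and SAP*

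**What the plan says.** Section 7 (Dose modifications for Adverse Events) ends with eight event tables. In the HIV Viremia table, both rows above 400 copies/mL carry the same instruction: "Repeat measurement in 4 weeks. Hold next cycle until plasma HIV RNA < 400 copies/mL". The row above 1000 adds a drug-resistance work-up if the repeat is again above 1000. A separate row takes participants with a DLT off therapy. The table closes with "Patients requiring a delay of >72 hours should go off protocol therapy", and makes no exception for viremia.

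The 72-hour line stands under all eight tables. The sentence introducing them lists only seven events: "Below are dose management tables for the following AEs: fatigue, nausea, vomiting, diarrhea, neutropenia, thrombocytopenia, and hepatic damage". HIV viremia is not among them.

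Section 6.4 has a general stopping criterion, "Dosing interruption lasting >12 weeks", and states the 27-week treatment duration for participants without adverse-event delays. Study Calendar footnote a sets 9-week cycles with a dosing window of ±2 days. Footnote k lets laboratory tests after Cycle 1 be drawn up to 72 hours early.

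**The concern.** One part of the table describes hold and resume: wait for a test 4 weeks later and dose once HIV RNA is below 400. The other part ends treatment after a delay of 3 days. When a due dose is withheld for that test, the second rule removes the participant before the first can operate.

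At stake is whether an HIV-positive participant with viremia may resume or loses all remaining doses. Two sites could treat the same participant in opposite ways, each citing the protocol. This changes exposure in cycles 2 to 4 and the adverse events observed there. Section 9.1.1.1 counts adverse events after day 28 among the considerations for the recommended phase 2 dose, in a trial of up to 20 participants.

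**Working it through.** The plan gives no figure to reproduce. The check is calendar arithmetic.

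**Inputs**
- Retest interval 4 weeks = 28 days = 672 h; delay limit 72 h = 3 days (Section 7).
- Doses at weeks 0, 9, 18 and 27, window ±2 days (Study Calendar, footnote a).
- Viral-load draws at screening, weeks 0, 4, 9, 13, 18 and 27, and end of treatment. This is my reading of the Study Calendar row, whose column alignment is inferred from the extracted table.
- Draws after Cycle 1 may be taken up to 72 h early (footnote k).

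**Formula:** delay = day of the repeat that could release the dose − day the dose is due.

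**Case 1: result above 400 known before the dose at week 9, 18 or 27.** The draw is 0 to 3 days before the due dose and the repeat is 28 days after the draw.
- Delay = 28 − 3 = 25 days, up to 28 − 0 = 28 days, or 600 to 672 h.
- 600/72 = 8.3 and 672/72 = 9.3 times the limit.

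**Case 2: result above 400 at week 4 (or 13).** The repeat falls at week 8 (17), one week before the dose at week 9 (18).
- If the repeat is below 400, the dose is on time and there is no conflict.
- If viremia persists through the repeat and the dosing visit, the next 4-week repeat is at week 12 to 13 (21 to 22). Delay = 21 to 28 days. At 21 days this is 504 h, and 504/72 = 7.0 times the limit.

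**Shortest possible delay, using the windows in Case 2**
- Week 4 draw 2 days early: day 28 − 2 = 26; repeats at days 54 and 82; dose 2 due at latest on day 63 + 2 = 65; 82 − 65 = 17 days.
- Week 13 draw 72 h early: day 91 − 3 = 88; repeats at days 116 and 144; dose 3 due at latest on day 126 + 2 = 128; 144 − 128 = 16 days (384 h, 5.3 times).
- If the ±2-day window may be added to the 72 hours: day 86; repeats at days 114 and 142; 142 − 128 = 14 days (336 h, 4.7 times).

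**Dosing-day result known only after injection.** After week 9, 4-weekly repeats fall at weeks 13 and 17, before dose 3. After week 18 they fall at weeks 22 and 26, before dose 4. There is no delay unless viremia persists. After the week 27 injection no cycle remains to hold.

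**Doses at stake**

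| Dose held | Lost under the 72-hour line | Lost under hold and resume, repeat below 400 |
|---|---|---|
| 2 | 3 | 0 |
| 3 | 2 | 0 |
| 4 | 1 | 0 |

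The last column assumes that held doses are made up, which I infer from the 6.4 duration clause.

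**The other tables.** Three of the eight have a hold row: fatigue, neutropenia and HIV viremia. The fatigue and neutropenia holds fix no retest time, so they can end within 72 hours. Only the viremia table fixes an interval longer than the limit.

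**The case against.** The strongest reply is that the two lines can be obeyed in sequence: hold the dose, stop therapy once the delay exceeds 72 hours, and still repeat HIV RNA at 4 weeks for safety. A reader might infer that the table cannot be followed at all. The text does not support that, because the sequential reading is literally possible. But on that reading the hold-until-below-400 rule does nothing whenever a due dose awaits the ordered repeat.

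Other passages favor hold and resume. Section 2.1.5 reports that viral blips in an earlier IL-7 trial led to delayed doses, and that blips in another study lasted under 4 weeks. Section 2.4.1 names resistant virus and AIDS-defining events as the HIV stopping events, not viremia above 400 alone. In the table, only the DLT row orders removal.

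It is also fair that the conflict is conditional. No text requires a viral-load result before dosing; the explicit pre-dose check is the lymphocyte count. An unscheduled earlier retest is not forbidden, though the table does not provide for one. Events may be few: Section 3.1.5 says "HIV-positive patients must have undetectable HIV viral loads", and the blips reported in Section 2.1.5 were "HIV RNA blips >50 copies/mL, occasionally exceeding 200 copies/mL", with no mention of levels above the hold threshold. Real-time safety review by the protocol lead and coordinating center, and at least monthly investigator calls, should limit divergence between sites. These points bound the size of the problem but leave the contradiction in the table.

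**Conclusion.** Wrong as written, in a defined set of situations. Whenever a due dose is withheld pending the ordered 4-week repeat, the delay is weeks (21 to 28 days nominally, about 14 to 16 at the shortest) against a 3-day limit. The 72-hour line then always acts first, at a cost of 3, 2 or 1 doses.

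Three stronger inferences are not supported:
- That every result above 400 ends therapy. The working shows several routes with no delay.
- That the 28-day DLT assessment is compromised. The first dose that this rule can hold is at week 9, so the DLT count is essentially unaffected.
- That the line is a proven carry-over. The omission of viremia from the introductory list suggests it but does not establish it.

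The 12-week limit in 6.4 is not itself in conflict, since a shorter event-specific limit can coexist with it. The documents give no rate of HIV RNA above 400 on treatment, so I put no number on the participants affected. The conclusion rests on the calendar reading stated in the working and on the retest being done when the table orders it.

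**What to change.** In the HIV Viremia table only, delete the 72-hour line so that the 12-week limit in 6.4 governs the hold, or replace it with a stated limit longer than 4 weeks. Leave the line in the other seven tables. If the sponsor does want viremia above 400 to end therapy when a dose is due, the hold rows should say that instead. A short cross-reference in 6.4 to shorter limits in Section 7 would help.

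The edit is small but has costs:
- A participant with viremia may stay on hold for weeks. The DLT row and the other 6.4 criteria still apply.
- Persistent viremia needs further 4-weekly viral loads outside the Study Calendar. Counting from Case 1, repeats fall at delay days 25–28, 53–56 and 81–84; 12 weeks is 84 days, so the third is at the limit.
- A hold of 4 to 12 weeks moves dose 4 from week 27 to weeks 31 to 39. Footnote b sets the end-of-treatment visit at week 36 or sooner. That visit should move by the length of the hold, or a shorter cap should be chosen. A cap of 8 weeks allows two repeats and, for a single hold, puts dose 4 no later than week 27 + 8 = 35.
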